## **9.2 Handling of Missing Data**

For time-to-event endpoints, event and censoring details will be described in Section 9.3.

### **9.2.1 Missing Data due to COVID-19**

Missing data could occur due to various reasons, including missing visits/assessments, early withdrawal from the study, or missing due to COVID-19 infection or logistic restriction.

The COVID-19 pandemic is interfering with the conduct of many ongoing trials, with potential impacts on treatment duration and the collection, analysis, and the interpretation of clinical trial data. Some protocol-specified visits in the clinical trials may be impacted due to COVID-19 infection or logistical restrictions during the pandemic. Impacted visits due to COVID-19 will be recorded in the database. The probability of having missed visits and missing data due to COVID-19 infection or logistical restrictions related to the COVID-19 pandemic can be reasonably assumed to be unrelated to the unobserved values. Therefore, for the purpose of statistical analysis, it is reasonable to assume that these missing data are missing at random (MAR) and the statistical models that require MAR assumption are appropriate. Sensitivity analyses will be performed to assess the impact of missing data and the robustness of the conclusion.

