7.4 Statistical Analyses for Efficacy

Efficacy analysis will be performed by the subject's randomized treatment group. All statistical tests will be performed at a 2-sided significance level of 0.1. A 95% confidence interval (CI) of the treatment difference between each ABBV-154 dose and placebo will be provided. The actual value of stratification factors will be used in the analysis. Enrollment in the optional PK sampling is not expected to impact any of the efficacy endpoints and will thus not be used as a stratification factor in the analysis.

- For time-to-event endpoints, comparison of number of events will be made between each ABBV-154 dose and placebo based on log-rank test stratified by stratification factors. The point and CI estimate of median time to event and event-free rate for each group will be reported based on Kaplan-Meier curves. Hazard ratio and its corresponding CI for each ABBV-154 group compared with placebo will be estimated using Cox regression analysis adjusting for stratification factors. For all analyses of time-to-event endpoints, subject without an event at the time of the analysis will be administratively censored at the time of the last available assessment.
- For categorical variables, pairwise comparison will be made between each ABBV-154 dose and placebo using the Cochran-Mantel-Haenszel (CMH) test, adjusting for stratification factors. Nonresponder imputation incorporating multiple imputation (NRI-MI) to handle COVID-19 will be the primary approach to handle missing data for categorical endpoints.
- For continuous variables other than glucocorticoid dose, the comparison will be made between each ABBV-154 dose and placebo based on the mixed effect model repeated measures (MMRM) adjusting for visit, interaction between treatment and visit, actual values of stratification factors as fixed factors, and baseline value as a covariate. The MMRM will be the primary approach to handle missing values for continuous endpoints.
- For analyses of glucocorticoid dose, comparison will be made between each ABBV-154 dose and placebo based on the analysis of covariance (ANCOVA) adjusting for stratification factors as fixed factors, and baseline glucocorticoid dose as a covariate.

Summary and Analysis of the Primary Endpoints

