The primary endpoint is the time to flare. The time origin is the first dose of study drug and the time of first flare will be used for the analysis. Comparison of the primary endpoint will be made between each ABBV-154 dose and placebo using the log-rank test adjusting for stratification factors. The point and CI estimate of median time to flare and flare-free rate for each group will be reported based on Kaplan-

Meier curves. Hazard ratio and its corresponding CI for each ABBV-154 group versus placebo will be estimated using Cox regression analysis adjusting for stratification factors.

One supplementary analysis for the primary endpoints is to test a prespecified set of dose-response models among ABBV-154 dose groups and the placebo group at Week 24 using the Multiple Comparison Procedure – Modeling (MCP-Mod) method.

Summary and Analysis of Secondary Endpoints

Analysis of secondary endpoints are described above.

Summary and Analysis of Additional Efficacy Endpoints

Analysis of additional efficacy endpoints are described above.

Subgroup Analysis for Efficacy

To evaluate the consistency of efficacy across demographic and other baseline characteristics, the following subgroup analysis will be performed on the primary endpoint:

- Baseline glucocorticoid use (≥ 10 mg/day; < 10 mg/day prednisone equivalent)
- Length of prior glucocorticoid treatment for PMR (≤ 1 year; > 1 year)
- Age (\leq median; $>$ median)
- Sex (female; male)
- Race (white; nonwhite)

In addition, change from Baseline in glucocorticoid dose at Week 24 will be analyzed by the following subgroup:

- Glucocorticoid status at Week 24 (glucocorticoid free; not glucocorticoid free)

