## **9.0 Efficacy Analyses**

### **9.1 General Considerations**

All efficacy analyses will be conducted in the ITT Population in each period. In addition, Per-protocol analysis for the primary endpoint will be performed. All tests will be 2-sided at an alpha level of 0.1.

The Primary Analysis will be performed after all subjects have either completed the Week 24 visit or withdrawn from the study. This analysis will be the only and final analysis for the primary and secondary efficacy endpoints.

The primary endpoint will be analyzed using logrank test stratified by baseline stratification factors [Glucocorticoid use at Baseline ( $\geq 10$  mg/day;  $< 10$  mg/day prednisone equivalent); Length of prior glucocorticoid treatment for PMR ( $\leq 1$  year;  $> 1$  year)]. The point and 95% confidence interval (CI) estimate of median time to event and event-free rate for each group will be reported based on Kaplan-Meier curves. Hazard ratio and its corresponding 95% CI for each ABBV-154 group compared with placebo will be estimated using Cox regression analysis adjusting for Baseline stratification factors [Glucocorticoid use at Baseline ( $\geq 10$  mg/day;  $< 10$  mg/day prednisone equivalent); Length of prior glucocorticoid treatment for PMR ( $\leq 1$  year;  $> 1$  year)]. For all analyses of time-to-event endpoints, 1) subject without an event at the time of the analysis will be administratively censored at the time of the last available assessment or cutoff, whichever is later; 2) a flare at Baseline will not be counted as an event; 3) if a flare event and an intercurrent event happen on the same day, subject will be counted as having a flare event.

Unless otherwise specified, the categorical endpoints and continuous endpoints will be analyzed by Cochran-Mantel-Haenszel (CMH) and Mixed-Effect Model Repeat

Measurement (MMRM), respectively, and the corresponding analyses are specified in Section 9.2.

Unless otherwise specified, any subject who is randomized based on a wrong stratum will be analyzed according to the actual stratum the subject belongs to.

"Baseline" refers to the last non-missing observation on or before the day of the first administration of study drug or randomization if no study drug is given. Observation on the same day as the first administration of study drug will be considered for the baseline, regardless of whether observation time (if available) was before or after the first administration of study drug time.

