## 9.2.2 Handling of Intercurrent Events and Missing Data in Categorical and Continuous Endpoints

- Non-Responder Imputation incorporating multiple imputation to handle COVID-19 (NRI-MI) will be the primary approach to handle missing data for categorical endpoints. The NRI-MI will categorize any subject who does not have an evaluation during a pre-specified visit window (either due to missing assessment, due to early withdrawal from the study, or due to intercurrent event) as a non-responder for the visit. The only exceptions are: 1) when the subject is a responder both before and after the visit window, the subject will be categorized as a responder for the visit. 2) missing data due to COVID-19 infection or logistical restriction will be handled by Multiple Imputation. In addition, all assessments after the start of intercurrent events will not be included in the analyses; as a result, subjects will be counted as non-responders thereafter and will not be imputed by MI.
- Non-Responder Imputation (NRI): In the interim analyses, NRI may be used due to subjects being in the study for different durations which makes multiple imputation infeasible.
- Multiple Imputation (MI): Markov Chain Monte Carlo (MCMC) will be first applied to augment data into monotonic missing pattern and PROC MI will be used to generate 30 datasets using the regression method. The variables to be included in the imputation model are treatment group, stratification factors at randomization [Glucocorticoid use at Baseline ( $\geq 10$  mg/day;  $< 10$  mg/day prednisone equivalent); Length of prior glucocorticoid treatment for PMR ( $\leq 1$  year;  $> 1$  year)], Baseline, and measurements at each visit. The random seed for MCMC and the random seed for PROC MI are specified in Appendix C. The imputed post-baseline measurements will be rounded to the same precision as the observed data before the determination of responder status. Subjects will be characterized as responders or non-responders based on MI imputed datasets. Using the Cochran-Mantel-Haenszel (CMH) model adjusted by stratification factors [Glucocorticoid use at Baseline ( $\geq 10$  mg/day;  $< 10$  mg/day prednisone equivalent); Length of prior glucocorticoid treatment for PMR ( $\leq 1$  year;  $> 1$  year)], the imputed endpoints will be analyzed using each of the 30 datasets. SAS PROC MIANALYZE will be used to generate the final inferences of the risk difference between each ABBV-154 group and

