placebo. Note that measurements will be considered as missing after the start of confounding medication before MI. Regardless of MI imputed values, subjects after receiving confounding medication will be counted as non-responders.

Efficacy assessments after the initiation of rescue medication, immunomodulator or violation of protocol-allowed systemic glucocorticoid use will not be included in the analyses. As a result, the subjects will be considered as non-responders in the NRI-MI approach.

- **Mixed-Effect Model Repeat Measurement (MMRM):** MMRM will be the primary approach to the analysis of continuous variables except for glucocorticoid dose. The repeated measures analysis will be conducted using a mixed model including observed measurements at all visits. Subject's observations after intercurrent events will not be used in the MMRM. The mixed model includes the categorical fixed effects of treatment, visit and treatment-by-visit interaction, stratification factors at randomization [Glucocorticoid use at Baseline ( $\geq 10$  mg/day;  $< 10$  mg/day prednisone equivalent); Length of prior glucocorticoid treatment for PMR ( $\leq 1$  year;  $> 1$  year)], and the continuous fixed covariates of baseline measurement. An unstructured variance-covariance matrix (UN) will be used. If the model does not converge, an alternative variance-covariance structure matrix (e.g., autoregressive (1) or compound symmetry) will be used. Parameter estimation is based on the assumption of data being missing at random and the method of restricted maximum likelihood (REML) will be used.
- **Analysis of covariance (ANCOVA):** ANCOVA will be the primary approach for the analysis of glucocorticoid dose. No intercurrent event will be considered in the analysis of glucocorticoid dose. The ANCOVA model includes the categorical fixed effects of treatment and stratification factors at randomization [Glucocorticoid use at Baseline ( $\geq 10$  mg/day;  $< 10$  mg/day prednisone equivalent); Length of prior glucocorticoid treatment for PMR ( $\leq 1$  year;  $> 1$  year)], and baseline glucocorticoid dose as a covariate.
- **As Observed (AO):** The AO analysis will not impute values for missing evaluations, and thus a subject who does not have an evaluation on a scheduled

visit will be excluded from the AO analysis for that visit. AO will include all values collected in the study.

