**9.3.3 Sensitivity and Supplementary Analyses of the Primary Efficacy Endpoint(s)**

Not applicable.

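### SAP 9.2.1 promises sensitivity analyses for missing data, but 9.3.3 and 9.4.3 specify none, so no planned analysis varies the censoring assumption behind time to flare

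*SAP*

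**What the plan says.** SAP 9.2.1, under the COVID-19 heading, argues that pandemic-related missing data may be treated as missing at random. It then commits in general terms: "Sensitivity analyses will be performed to assess the impact of missing data and the robustness of the conclusion". It names no method, endpoint or population.

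SAP 9.3.3 is where sensitivity and supplementary analyses of the primary endpoint would be listed. Its whole content is "Not applicable". SAP 9.4.3, for the secondary endpoints, has the same entry.

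Other parts of the plan bear on the point:

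- SAP 9.1 adds a per-protocol run: "In addition, Per-protocol analysis for the primary endpoint will be performed".
- Protocol 7.4 adds MCP-Mod: "One supplementary analysis for the primary endpoints is to test a prespecified set of dose-response models". SAP 9.6 describes it.
- SAP 9.2.2 defines an As Observed method ("The AO analysis will not impute values for missing evaluations") and ties it to no endpoint.
- For categorical endpoints, SAP 9.2.2 classes a subject without an evaluation "as a non-responder for the visit". The exceptions are gaps between two responder visits and COVID-19 missingness, which is multiply imputed.
- For time to flare, SAP 9.1 has subjects without an event "administratively censored at the time of the last available assessment or cutoff, whichever is later". Protocol 7.4 says they "will be administratively censored at the time of the last available assessment", with no mention of cutoff. SAP 2.1 and 8.0 agree with the protocol.

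**The concern.** The primary log-rank test is valid only if subjects censored without a flare have the same future flare risk as those still followed in their arm. In a steroid-taper trial that can fail. Subjects may leave because symptoms are returning or because of adverse events. Time to flare is also censored at the start of an immunomodulator, and Protocol 5.5 lists the need for one to treat PMR as a reason to stop study drug. Some censoring may therefore mark worsening disease. SAP Table 1 labels this estimand composite, although its rule is to censor and not to count an event.

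SAP 9.1 makes the Week 24 analysis the only and final one for the primary and secondary endpoints, and SAP 12.0 plans an interim analysis under a separate unblinding plan. Sensitivity analyses chosen after results are visible carry less weight. As the SAP stands, a dose could be reported as effective without showing whether that survives a reasonable assumption about the subjects who left.

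**Working it through.** **1. The plan's own figures** (Protocol 7.10, SAP 2.4: 37 flares in the top-dose and placebo arms, 70% and 30% flare-free by Week 36, two-sided 0.1, 40 per arm).

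- Hazard ratio: ln(0.70)/ln(0.30) = 0.296. This reproduces.
- Power (Schoenfeld): Φ(√37/2 × |ln 0.296| − 1.645) = Φ(3.703 − 1.645) = 98.0%. Freedman: Φ(√37 × 0.704/1.296 − 1.645) = 95.1%. The stated power above 90% holds.
- Flares in that pair by Week 36 without loss: 40 × 0.70 + 40 × 0.30 = 40, against 37 stated (37/40 = 0.925).
- All four arms, if the Emax model (ED50 150 mg) is applied to flare proportions: 0.700, 0.579, 0.412 and 0.300. Then 40 × 1.990 = 79.6, against 74 stated (0.929).

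A reduction of about 7% is therefore built in without explanation. It could be loss or incomplete Week 36 follow-up, so it cannot be read as a withdrawal rate.

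**2. Does any planned analysis vary the censoring?**

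- Per-protocol: removes subjects with major deviations and keeps the same censoring rule.
- MCP-Mod: uses summary rates from the primary analysis approach (SAP 9.6), so it inherits the censoring.
- As Observed: assigned to no endpoint.
- SAP 9.2 defers event and censoring details to 9.3, but Table 1 there covers only the two intercurrent events and not withdrawal.
- Flare-free up to Week 24: same flare event, same ITT population, most non-COVID loss counted as failure. This is an indirect check.
- The two glucocorticoid-dose endpoints: ANCOVA with no rule for missing dose data (SAP 9.2.2) and no alternative analysis.

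**3. Illustration of size.** From the plan: 40 per arm, two-sided 0.1 (so 5% in the direction of benefit), placebo hazard −ln(0.30)/36 = 0.0334 per week up to Week 36. Assumed: no true effect, uniform 20-week accrual, data cut when the last subject reaches Week 24, unstratified log-rank, and loss in one active arm only, just before a flare would be recorded. Chance of declaring benefit for that arm:

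| Would-be flares lost (subjects of 40) | Censored at loss | Censored at cutoff (SAP 9.1 read literally) | Counted as flares |
|---|---|---|---|
| 0 | 5% | 5% | 5% |
| 10% (about 3) | about 10% | about 15% | about 5% |
| 20% (about 5) | about 20% | about 31% | about 5% |
| 30% (about 8) | about 33% | about 54% | about 5% |

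These are Monte Carlo figures, and repeat runs agree to within a point or two. A separate simulation with a fixed Week 24 horizon, again losing 10%, 20% and 30% of would-be flares (5%, 11% and 16% of the active arm), gave about 10%, 18% and 31% with censoring at loss, and about 12%, 27% and 45% with censoring at cutoff.

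The cutoff column is worse because, under the later-of-the-two rule, an early withdrawal stays in the risk set as flare-free until the data cut.

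**4. The indirect check.** In the same null scenario, a Week 24 flare-free comparison with losses counted as non-response stayed at about 4% to 5%. It would disagree with a distorted log-rank result.

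**The case against.** Four arguments on the other side carry weight.

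- **The plan is not without any check.** A reader might infer from the two empty sections that nothing guards against informative loss. The documents do not support that. Flare-free up to Week 24 already counts most such loss as failure. SAP 9.3.3 is also not the full list of extra primary analyses, since per-protocol and MCP-Mod sit elsewhere. What remains is that neither of those two varies the censoring, and the flare-free comparison does not test the log-rank or hazard-ratio result itself.
- **The promise may be narrow.** It sits in the COVID-19 subsection, straight after the missing-at-random argument. Extending it to all missing data is a reading, though that subsection also lists early withdrawal and the sentence is general. On the narrow reading it is still undelivered.
- **Conduct rules work against unrecorded flares.** Subjects who stop study drug are encouraged to keep attending (Protocol 5.6). Flares can be confirmed at unscheduled visits, rescued subjects continue on study drug, and a recommendation to raise the dose is recorded even if the subject declines (Protocol 5.8). Complete loss of flares in one arm is therefore a worst case.
- **This is Phase 2 without overall Type I error control** (SAP 13.0). That limits the consequence but does not remove the internal conflict.

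**Conclusion.** The conflict between SAP 9.2.1 and SAP 9.3.3 and 9.4.3 is real. For time to flare, no analysis that varies the censoring assumption is specified. The two glucocorticoid-dose endpoints have neither a missing-data rule nor a sensitivity analysis. Flare-free up to Week 24 is mostly covered by its main rule.

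The size rests on assumed loss. In the worst direction, about 3 to 8 unrecorded flares among 40 subjects move a 5% error to about 10% to 33% with censoring at loss, and to about 15% to 54% under the literal SAP 9.1 clause. A reader might take these as forecasts or as evidence that the result will be biased. The documents support neither: they give no withdrawal rate and no sign that loss will fall on one arm. The figures show only that a handful of losses can matter at this sample size. This is a cheap improvement and does not invalidate the design.

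**What to change.** 1. **SAP 9.1.** Reconcile the censoring clause (later of last assessment and cutoff) with Protocol 7.4 and SAP 2.1 and 8.0 (last available assessment). This comes first, because under the literal clause withdrawals are censored at cutoff and could not be picked out by an early censoring date.
2. **SAP 9.3.3.** Replace the present entry with:
   - the stratified log-rank test and Cox model repeated with some subjects recoded as flares. These are subjects in any arm who, before Week 24 and without a flare, withdraw or have an immunomodulator or glucocorticoid-violation intercurrent event. The flare is dated at the last available assessment or the event date;
   - a tipping-point analysis by multiple imputation of residual time to flare, raising the post-censoring hazard in the ABBV-154 arm until significance is lost;
   - cross-references to the per-protocol and MCP-Mod analyses.
3. **SAP 9.4.3.** Add a missing-data sensitivity analysis for the two glucocorticoid-dose ANCOVAs, for example multiple imputation with a delta adjustment. Assign As Observed to flare-free up to Week 24.

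The cost is SAP wording and a few extra tables, with no new data or subjects. Some results may look less favourable. The losses-as-flares run is conservative when loss is random, so loss of significance there does not by itself show bias and should be read beside the tipping-point result.

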## 9.2.2 Handling of Intercurrent Events and Missing Data in Categorical and Continuous Endpoints

- Non-Responder Imputation incorporating multiple imputation to handle COVID-19 (NRI-MI) will be the primary approach to handle missing data for categorical endpoints. The NRI-MI will categorize any subject who does not have an evaluation during a pre-specified visit window (either due to missing assessment, due to early withdrawal from the study, or due to intercurrent event) as a non-responder for the visit. The only exceptions are: 1) when the subject is a responder both before and after the visit window, the subject will be categorized as a responder for the visit. 2) missing data due to COVID-19 infection or logistical restriction will be handled by Multiple Imputation. In addition, all assessments after the start of intercurrent events will not be included in the analyses; as a result, subjects will be counted as non-responders thereafter and will not be imputed by MI.
- Non-Responder Imputation (NRI): In the interim analyses, NRI may be used due to subjects being in the study for different durations which makes multiple imputation infeasible.
- Multiple Imputation (MI): Markov Chain Monte Carlo (MCMC) will be first applied to augment data into monotonic missing pattern and PROC MI will be used to generate 30 datasets using the regression method. The variables to be included in the imputation model are treatment group, stratification factors at randomization [Glucocorticoid use at Baseline ( $\geq 10$  mg/day;  $< 10$  mg/day prednisone equivalent); Length of prior glucocorticoid treatment for PMR ( $\leq 1$  year;  $> 1$  year)], Baseline, and measurements at each visit. The random seed for MCMC and the random seed for PROC MI are specified in Appendix C. The imputed post-baseline measurements will be rounded to the same precision as the observed data before the determination of responder status. Subjects will be characterized as responders or non-responders based on MI imputed datasets. Using the Cochran-Mantel-Haenszel (CMH) model adjusted by stratification factors [Glucocorticoid use at Baseline ( $\geq 10$  mg/day;  $< 10$  mg/day prednisone equivalent); Length of prior glucocorticoid treatment for PMR ( $\leq 1$  year;  $> 1$  year)], the imputed endpoints will be analyzed using each of the 30 datasets. SAS PROC MIANALYZE will be used to generate the final inferences of the risk difference between each ABBV-154 group and

placebo. Note that measurements will be considered as missing after the start of confounding medication before MI. Regardless of MI imputed values, subjects after receiving confounding medication will be counted as non-responders.

Efficacy assessments after the initiation of rescue medication, immunomodulator or violation of protocol-allowed systemic glucocorticoid use will not be included in the analyses. As a result, the subjects will be considered as non-responders in the NRI-MI approach.

- **Mixed-Effect Model Repeat Measurement (MMRM):** MMRM will be the primary approach to the analysis of continuous variables except for glucocorticoid dose. The repeated measures analysis will be conducted using a mixed model including observed measurements at all visits. Subject's observations after intercurrent events will not be used in the MMRM. The mixed model includes the categorical fixed effects of treatment, visit and treatment-by-visit interaction, stratification factors at randomization [Glucocorticoid use at Baseline ( $\geq 10$  mg/day;  $< 10$  mg/day prednisone equivalent); Length of prior glucocorticoid treatment for PMR ( $\leq 1$  year;  $> 1$  year)], and the continuous fixed covariates of baseline measurement. An unstructured variance-covariance matrix (UN) will be used. If the model does not converge, an alternative variance-covariance structure matrix (e.g., autoregressive (1) or compound symmetry) will be used. Parameter estimation is based on the assumption of data being missing at random and the method of restricted maximum likelihood (REML) will be used.
- **Analysis of covariance (ANCOVA):** ANCOVA will be the primary approach for the analysis of glucocorticoid dose. No intercurrent event will be considered in the analysis of glucocorticoid dose. The ANCOVA model includes the categorical fixed effects of treatment and stratification factors at randomization [Glucocorticoid use at Baseline ( $\geq 10$  mg/day;  $< 10$  mg/day prednisone equivalent); Length of prior glucocorticoid treatment for PMR ( $\leq 1$  year;  $> 1$  year)], and baseline glucocorticoid dose as a covariate.
- **As Observed (AO):** The AO analysis will not impute values for missing evaluations, and thus a subject who does not have an evaluation on a scheduled

visit will be excluded from the AO analysis for that visit. AO will include all values collected in the study.

